2.9.1.2 Modified Crichton Scale

Modified Crichton Scale total score is defined as the sum of 7 items. If at least one missing item exists, the total score is set as missing..

Modified Crichton Scale total score will be summarized at visits 2, 3, 4, 6 and 8.

For change from baseline (visit 2), summary statistics and 95% CI of the mean will be derived for FAS at visits 3, 4, 6 and 8.

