#### **6.4.2 Neuropsychiatric Inventory-10 (NPI-10):**

NPI-10 will be conducted at Visit 2, 4 and 8 (refer [Table 6-1](#)). NPI-10 at premature discontinuation will not be conducted if patient discontinues because of adverse event.

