**6.4.5 Modified Crichton Scale**

Modified Crichton scale will be conducted at Visit 2, 3, 4, 6 and 8 (refer [Table 6-1](#)). Modified Crichton scale at premature discontinuation will not be conducted if patient discontinues because of adverse event.

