2.1.1.4 Post-baseline assessments

Post-baseline values are defined as assessments taken after the start of study treatment.

When change from baseline is of interest the following formula will be used for each scheduled visit and time-point where baseline and post-baseline values are both available: **Change from baseline = post-baseline value – baseline value.**

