2.5.2 Statistical hypothesis, model, and method of analysis

The change from baseline in MMSE total score will be analyzed using a mixed model repeated measures (MMRM) model. The model will contain visit as a fixed effect, baseline MMSE score as a covariate and subject as a random effect. An unstructured covariance matrix should be used. The estimated mean change at Week 24 along with a two-sided 95% confidence interval and p-value will be tabulated and presented graphically. P-values will be used in descriptive manner.

Further, the MMSE total score and change from baseline will be summarized using standard descriptive statistics by visits.

In addition, the primary endpoint will be summarized and analyzed by subgroups specified in [Section 2.2.1.1](#).

The MMRM model of subgroup analysis will contain visit, subgroup (categories) and visit*subgroup as fixed effects, baseline MMSE score as a covariate and subject as a random effect. An unstructured covariance matrix should be used. The estimated mean change at Week 24 along with a two-sided 95% confidence interval and p-value will be presented. P-values will be used in descriptive manner. Figures will only be provided for selected subgroup analysis as specified in [Section 2.2.1.1](#).

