2.5.3 Handling of missing values/censoring/discontinuations

The primary analysis will be performed using a MMRM model, which assumes that missing data is missing at random (MAR) given the preceding observed data.

The discontinuations data has been handled as explained in Section 4, point 3. No other imputation methods will be considered.

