2.9.1.1 Neuropsychiatric Inventory (NPI) score

The neuropsychiatric symptoms will be assessed by the 10-item Neuropsychiatric Inventory (NPI). The NPI-10 total score is a sum of the 10 domains, where the score for a domain is defined as the product of frequency (range: 1-4) and severity (range: 1-3). Each domain has a maximum score of 12 and all domains are equally weighted for the total score (thus the range for the total score is 0 to 120). The NPI-10 total score and individual domain scores will be summarized descriptively at visits 2, 4 and 8 respectively. For where, N/A or absent has been marked in the crf, value 0 is considered for the same.

For change from baseline in NPI-10 total score at Week 24, summary statistics and 95% CI of the mean change will be derived for FAS.

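### The Week 24 changes in Modified Crichton and NPI-10 use only patients with a value mapped to that visit. An MMRM like the one for MMSE would also use the earlier ratings of patients who leave.

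*SAP*

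**What the plan says.** **Analysis of the two scales.** For change in Modified Crichton, SAP 2.9.1.2 specifies "summary statistics and 95% CI of the mean will be derived for FAS at visits 3, 4, 6 and 8". For the Week 24 change in NPI-10 total score, SAP 2.9.1.1 specifies "summary statistics and 95% CI of the mean change will be derived for FAS". SAP 2.1.1.4 computes a change only "where baseline and post-baseline values are both available". A missing Crichton item removes the whole total: "If at least one missing item exists, the total score is set as missing". Protocol 9.5.1 plans the same kind of summaries, so the SAP follows the protocol here.

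**Ratings collected.** Protocol 6.4.5: "Modified Crichton scale will be conducted at Visit 2, 3, 4, 6 and 8", which is four post-baseline ratings. Protocol 6.4.2: "NPI-10 will be conducted at Visit 2, 4 and 8", which is two.

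**MMSE.** SAP 2.5.2 fits an MMRM: "The model will contain visit as a fixed effect, baseline MMSE score as a covariate and subject as a random effect", with unstructured covariance. SAP 2.5.3 gives the assumption: "The primary analysis will be performed using a MMRM model, which assumes that missing data is missing at random (MAR) given the preceding observed data". SAP 2.6.1.1 uses the same model for MMSE at Week 8, a secondary endpoint. SAP 2.5.4 adds completer and LOCF analyses for MMSE. No missing-data method is given for Crichton or NPI-10.

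**Leaving the study.** Protocol 5.6.2 lists worsening of the disease as a ground for stopping treatment. Protocol 6 asks for final-visit assessments from patients who leave early, but Protocol 6.4 drops the efficacy scales when the reason is an adverse event. SAP 4, item 3, moves exit records to the planned visit nearest the exit date.

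**The concern.** A patient who leaves after Week 16 can have three Crichton change scores, and none of them informs the Week 24 mean. A patient rated at an early exit is counted at the earlier visit to which the record is mapped, and is absent from Week 24 unless the exit fell close to it. If those who leave tend to be doing worse, the patients left at Week 24 are a better-off selection. Higher scores are worse on both scales, so the error flatters the treatment.

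Two features make this worth raising. The trial has one arm, so dropout bias cannot cancel between groups and the change from baseline is the whole result. Patients can also qualify through worsening behaviour or daily function (Protocol 4.1, criterion 9-1), and these are the domains the two scales measure.

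**Working it through.** **1. The plan's own figure.** SAP 3 gives SD 3.0, half-width 0.6, 97 evaluable and 120 enrolled.

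- n = (1.96 × 3.0 / 0.6)² = 96.04, rounded up to 97. This reproduces.
- Implied loss L = (120 − 97)/120 = 23/120 = 19.2%.
- In SD units, the half-width at n = 97 is 1.96/√97 = 0.199 SD. This is the yardstick below.

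**2. How loss turns into bias.** With fraction L lost, the observed-case mean is off by −[L/(1 − L)] × (how much worse the leavers would have been at Week 24). Here L/(1 − L) = 23/97 = 0.237. With one interim rating, dropout depending on it and correlation ρ, leavers who are d SD worse at that rating would be about ρd worse at Week 24. A bias of 0.069 SD at ρ = 0.6 therefore corresponds to d = 0.069/(0.237 × 0.6), about 0.49 SD.

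**3. Simulation if all loss depends on the last score (MAR).** Assumptions, none of them from the documents: normal change scores, equal correlation between visits, and every patient rated at the first post-baseline visit. Crichton has four visits and NPI-10 two. Loss is 19.2%, with 200,000 patients per scenario. Entries are the Week 24 observed-case bias in SD units; negative means too favourable.

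| Scale | ρ | Odds ratio 1 | 1.5 | 2 | 3 (per SD) |
|---|---|---|---|---|---|
| Crichton | 0.4 | 0.001 | −0.034 | −0.059 | −0.083 |
| Crichton | 0.6 | 0.003 | −0.052 | −0.084 | −0.122 |
| Crichton | 0.8 | 0.001 | −0.066 | −0.110 | −0.161 |
| NPI-10 | 0.4 | −0.001 | −0.032 | −0.048 | −0.071 |
| NPI-10 | 0.6 | 0.002 | −0.048 | −0.069 | −0.103 |
| NPI-10 | 0.8 | −0.001 | −0.059 | −0.098 | −0.145 |

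The likelihood-based mean, which is what an MMRM estimates, was off by at most 0.006 SD in all of these. That is expected, because the dropout was simulated as MAR.

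With the narrower assumptions of ρ 0.5–0.7, odds ratio 1.6–2.7 and 17–19% loss, the bias is about 0.04–0.13 SD. As a share of the half-width: 0.04/0.199 = 20% and 0.13/0.199 = 65%.

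**4. If most loss is unrelated to outcome.** Protocol 1.1 reports 16/107 = 15.0% stopping for adverse events in the earlier 1-step arm. Suppose 15.0 of the 19.2 points are unrelated to the scales, leaving 4.2 that depend on the last score. Scaling step 3 by 4.2/19.2 = 0.22 gives 0.04 × 0.22 = 0.009 to 0.13 × 0.22 = 0.029 SD. Direct simulation with ρ 0.5–0.7 gives about 0.01–0.03 SD (0.031 at the top of one run). As a share: 0.01/0.199 = 5% and 0.031/0.199 = 16%.

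**5. If dropout depends on the unobserved next score (MNAR).** Same range of ρ and odds ratios as the table, all loss outcome-related:

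| Scale | Observed-case bias (SD) | Bias left after the likelihood analysis (SD) |
|---|---|---|
| Crichton | 0.05–0.17 | 0.01–0.08 |
| NPI-10 | 0.07–0.18 | 0.03–0.15 |

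The model was less biased in every such scenario, but the gain is smaller for NPI-10, which has only one interim rating.

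**The case against.** The strongest reply is that the only dropout evidence in the documents points to adverse events. Protocol 1.1 names application-site reactions among the events leading to discontinuation in the earlier pivotal study, and skin reactions have no obvious link to daily function or behaviour. That stands as a plausible scenario, and it is why the size must include step 4 and zero. That adverse-event loss is unrelated to the scales is itself an assumption.

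A reader might infer that the ratings of worsening patients are thrown away. The documents do not say so. Only adverse-event exits skip the efficacy scales. Other leavers are due a final rating, and a Crichton rating mapped to Visit 3, 4 or 6 is reported there with a confidence interval. A late exit can be mapped to Week 24, so the estimate is observed-case and not strictly a completer mean. What stands is that the Week 24 estimate makes no use of those earlier scores.

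It is also fair that the trial does not aim to show superiority or non-inferiority (Protocol 3.2), that even the primary p-values are descriptive, and that summarising secondary scales is common. This lowers the priority. It does not fully explain the difference in treatment, because the secondary Week 8 MMSE endpoint does get the MMRM.

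**Conclusion.** The point holds as a conditional one. The Week 24 means for both scales are observed-case estimates with no missing-data method. They are too favourable if loss is related to worsening. Listing worsening as a ground for stopping makes that foreseeable, but does not establish it.

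- **Loss unrelated to outcome:** bias about zero.
- **Mostly unrelated adverse-event loss:** about 0.01–0.03 SD, 5–16% of the half-width.
- **All of a 17–19% loss driven by the last score:** about 0.04–0.13 SD, 20–65% of the half-width. The wider grid in step 3 runs from 0.03 to 0.16 SD.

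The SDs, correlations and dropout mechanism are all assumed. Two stronger readings are not supported. The first is that these results are known to be biased: nothing in the documents gives the mechanism. The second is that an MMRM removes the bias: it does so only under MAR. The endpoints are secondary and descriptive, and the primary MMSE analysis is unaffected.

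**What to change.** In SAP 2.9.1.1 and 2.9.1.2, estimate the mean changes with the model form of SAP 5.3.1: visit, baseline and unstructured covariance. The code does not carry over unchanged, because its outcome and baseline are defined as MMSE; replace both with the scale's own. Use Visits 3, 4, 6 and 8 for Crichton and Visits 4 and 8 for NPI-10. The NPI-10 model also supplies the Week 8 change, which SAP 1.2 lists as an endpoint but SAP 2.9.1.1 gives no change analysis for. Confirm that NPI-10 exit ratings are mapped to a visit in the model. Keep the observed-case summaries, labelled as descriptive. QOL-AD has one scheduled post-baseline visit and can stay as it is.

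Add three statements:

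- The analysis relies on MAR.
- Under MNAR it reduces bias but does not remove it, with less gain for NPI-10.
- Patients with no post-baseline rating contribute to neither method.

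The cost is SAP wording and two further model runs, with no new data. Model-based and raw means will differ somewhat, so each needs a clear label.

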2.9.1.3 Formulation usability questionnaire

This questionnaire data is used to assess if the usability rivastigmine patch is preferred by the majority (greater than 50%) of AD patient caregivers or not. This will be assessed using the questionnaire in the CRF. The proportion of caregivers preferring the patch will be summarized with two-sided 95% confidence intervals for the FAS.

In addition, reasons for questionnaire answers will be summarized by presenting the frequencies of endorsed reasons.

2.10 Clinician-reported outcomes

The following secondary endpoint related to clinician reported outcome will be analyzed:

2.10.1.1 J-CGIC

J-CGIC is a global assessment scale to assess change of the patient's clinical symptoms, which are assessed subjectively by clinicians with seven grades. (1: Marked improvement, 2: Moderate improvement, 3: Mild improvement, 4: Unchanged, 5: Mild Worsening, 6: Moderated Worsening, 7: Marked Worsening). The number and percentage of patients in each grade will be displayed at visits 3, 4, 6 and 8. Also, proportion and 95% confidence interval for the proportions of the patients without worsening (1: Marked improvement, 2: Moderate improvement, 3: Mild improvement, 4: Unchanged) and with improvement (1: Marked improvement, 2: Moderate improvement, 3: Mild improvement) will also be provided.

2.11 Other analyses

2.11.1 Treatment retention during the last 8 weeks of maintenance period:

Treatment retention rate will be summarized for the FAS.

Here, "treatment retention" is considered to be successful when a patient meets all of the following condition:

- complete the study,
- receive rivastigmine 18 mg treatment during the last 8 weeks of maintenance period,
- never decrease the dose during the last 8 weeks of maintenance period,

[figure not shown]
- comply with drug application $\geq 75\%$ during the last 8 weeks of maintenance period (compliance will be categorized as Poor ($<25\%$)), Average ($\geq 25\%$ to $<50\%$), Good ($\geq 50\%$ to $<75\%$), Very good ($\geq 75\%$ to $\leq 100\%$) and Overdose or misuse ($>100\%$)).

As stated in Section 2.2.1, Subgroup analysis, change from baseline in MMSE score at Week 24 and adverse events will be summarized by subgroup of patients satisfying treatment retention (yes/no).

Further, treatment retention rate will be summarized in these subgroups as below:

- Patient profile analysis 1a: Use of skin moisturizer at baseline (yes/no)*
 - ◆ Total
 - ◆ Compliance to study medication (<75% and 75-100%)
- Patient profile analysis 1b: Use of skin management at least one time during study period (yes/no)*
 - ◆ Total
 - ◆ Compliance to study medication (<75% and 75-100%)

Note: skin moisturizer or other skin management will be obtained from the prior and concomitant medication CRF as captured in the database and confirmed by the study medical experts.

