2.2.1.2 Subgroup analyses for safety endpoints

The following subgroup analyses will be performed for all adverse events summaries as mentioned in Section 2.6.2.1:

- age (\leq 65 years, $>$ 65 years)
- weight ($</\geq$ 40 kg, $</\geq$ 50 kg, $</\geq$ 60 kg)
- treatment regimen (overall, 1-step and 3-step titration)
- reason for switching to 3-step titration (as captured in the DAR page of CRF, e.g., adverse events, lab or test abnormality, lack of efficacy etc.)
- Patients satisfying treatment retention criteria as in Section 2.9.1 (yes/no)
- overall compliance to study medication (<75% and 75-100%)
- Patient profile analysis 1a: Use of skin moisturizer at baseline (yes/no)*
 - ◆ Total
 - ◆ Compliance to study medication (<75% and 75-100%)

Note: skin moisturizer will be identified using the data captured in the prior and concomitant medication CRF page and confirmed by the clinical team.

- Patient profile analysis 1b: Use of skin management at least one time during study period (yes/no)*

- ◆ Total
- ◆ Compliance to study medication (<75% and 75-100%)

Note: skin management will be identified using the data captured in the prior and concomitant medication CRF page and confirmed by the clinical team.

Amongst AEs of special interest,

1. Gastrointestinal symptoms will be summarized by age, weight and patient profile analysis 1a and 1b subgroups as described above,
2. Application site skin reactions and irritations will be summarized by age, weight and patient profile analysis 1a and 1b subgroups as described above.

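### SAP 2.11.1 splits the retention rate at the same 75% compliance cut that helps define retention, so lower retention below 75% is partly built in; patients above 100% fall outside both strata

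*SAP*

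**What the plan says.** SAP 2.11.1 says that retention "is considered to be successful when a patient meets all of the following condition", and lists four:

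- completing the study;
- "receive rivastigmine 18 mg treatment during the last 8 weeks of maintenance period";
- having no dose reduction over that same stretch of time;
- the requirement to "comply with drug application" at a level of 75% or more in those same 8 weeks.

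The last condition has a lower limit and no upper one. Its own list of compliance categories includes a class above 100%, named as overdose or misuse. Protocol 9.6.3 sets the same threshold and also lists a class above 100%.

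The section continues: "Further, treatment retention rate will be summarized in these subgroups as below". The groups are moisturizer use at baseline and any skin management during the study (each yes/no). Each is shown in total and by "Compliance to study medication (<75% and 75-100", where the upper class stops at 100%. No measurement period is given for this split.

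The same two classes appear in SAP 2.2.1.1 (MMSE change) and 2.2.1.2 (adverse events). In 2.2.1.2 the stand-alone item reads "overall compliance to study medication (<75% and 75-100", again ending at 100%, and 2.2.1.1 has a matching item. SAP 2.4.1 tabulates the class above 100% and lists the reasons for it.

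**The concern.** One of the four components of the outcome is compliance of at least 75%. The table then divides patients at 75% compliance. A lower retention rate in the lower stratum would follow at least in part from how retention was defined. A reader could take it as evidence that good compliance sustains treatment.

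The second problem lies at the other end of the scale. A patient recorded above 100% meets the 75% condition and so can be a retention success, but has no row in the compliance breakdown. The strata then need not add up to the total. In the adverse-event tables of 2.2.1.2, over-users drop out of the compliance breakdown, which is where a safety reader would look for them.

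**Working it through.** The documents give no retention rate and no compliance distribution, so there is no planned figure to reproduce. The check is on the definitions.

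**Inputs.** Treatment lasts 24 weeks, or 168 days (Protocol 3.1). The last 8 weeks are 56 days, and 56/168 = 1/3. The first 16 weeks are 112 days. Only completers can be retained, so a full 168-day denominator is the relevant case.

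**Case A: stratum measured over the last 8 weeks.** Every patient below 75% fails the fourth condition. Retention in that stratum is exactly 0%.

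**Case B: stratum measured over the whole study.** Overall compliance = (16 × first-16-week + 8 × last-8-week)/24. The 75% line is 0.75 × 168 = 126 applied days.

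- *Retained but below 75% overall.* With a perfect last 8 weeks (56 days), the first 16 weeks must supply fewer than 126 − 56 = 70 of 112 days, that is, under 62.5%. With exactly 75% in the last 8 weeks, the first 16 weeks must be under 75%. So the lower stratum can show retention only from patients whose compliance rose late.
- *At or above 75% overall but not retainable.* With 50% in the last 8 weeks (28 days), 126 − 28 = 98 of 112 days (87.5%) in the first 16 weeks still puts the patient in the upper stratum.

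**How strong is the dependence in Case B?** An illustrative simulation drew compliance in the two periods from beta distributions with means 0.80, 0.85 and 0.90, linked with varying correlation. These inputs are assumptions, not figures from the documents. The table gives the share of each stratum that meets the last-8-week compliance condition, as a range over the three means.

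| Correlation | Below 75% overall | 75% or more overall |
|---|---|---|
| 0 | 50-70% | 77-91% |
| 0.5 | 32-44% | 85-94% |
| 0.7 | 24-34% | 89-95% |
| 0.9 | 14-19% | 94-97% |
| 1 | 0% | 100% |

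These shares are ceilings on retention, because the other three conditions still apply. A gap between strata appears even at zero correlation, since the last 8 weeks are part of the overall figure.

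**Upper stratum.** Under either case, completion, the 18 mg condition and the no-decrease condition still decide who is retained. Retention there is not fixed.

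**Above 100%.**

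| Rule | Patient above 100% |
|---|---|
| Retention condition (at least 75%, no cap) | satisfied |
| Stratum below 75% | not in it |
| Stratum 75-100% | not in it |
| Total row | included |

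The deviation rules do not clearly remove such patients. In SAP 5.2, deviation S05, whose examples include applying more patches than prescribed, carries code 49, which keeps the patient in all analyses. If k such patients are counted as retained among N in the FAS, the rate is higher by k/N than if they are not. Taking N = 120 (planned enrolment) or N = 97 (evaluable target) for scale, each patient moves it by 1/120 = 0.8 or 1/97 = 1.0 percentage points.

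**The case against.** A reader might infer that the retention-by-compliance result is largely fixed by definition and that the split should be deleted. The documents do not support that. SAP 2.11.1 leaves the period of the split open, but 2.2.1.1 and 2.2.1.2 label the same cut as overall compliance. SAP 2.2.1.1 also applies the identical skin-care breakdown to MMSE at Week 8 as well as Week 24, where a last-8-week measure would make little sense. Whole-study compliance is the natural reading, and under it the dependence is real but incomplete. The upper stratum is open under either reading. Compliance is nested within skin-care use, so the comparison of interest is probably skin care yes versus no at a given compliance level. Within 75-100% that comparison is informative and would be lost by deletion. All of this stands.

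It can also be said that the class above 100% is already tabulated, with reasons listed, under 2.4.1. That is true, but it does not put those patients back into the subgroup tables or show how many count as retained. A reader might also want the criterion rewritten as 75% to 100%. That would change a definition set in Protocol 9.6.3 and is more than the problem needs. Finally, a class above 100% could be too small for the subgroup MMRM, which is a fair limit on where to add it.

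**Conclusion.** The point holds as a minor one. Lower retention in the stratum below 75% is partly built in: wholly (0%) if both measures cover the last 8 weeks, and partially if the stratum is whole-study compliance. In the partial case, the size depends on how closely early and late compliance agree, which the documents do not tell us; the simulated shares only show the range under assumed inputs. The 75-100% stratum is not determined by the definition.

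The gap above 100% follows from the rules as written, whichever period is meant. Whether it changes any table depends on such patients occurring. Their number is unknown and may be small.

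The retention summary is descriptive. Neither the primary MMSE analysis nor the sample size is touched.

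**What to change.** 1. In SAP 2.11.1, state that the subgroup uses overall compliance.
2. For retention, either drop the contrast between below 75% and 75-100%, or footnote it as dependent on the retention definition. Keep skin care yes/no within 75-100%.
3. Add a row above 100% to the descriptive compliance subgroup tables in 2.2.1.1, 2.2.1.2 and 2.11.1. Fit it as a category in the subgroup MMRM only if there are enough patients.
4. Keep the protocol's criterion of at least 75%, but report the retention rate twice: with patients above 100% in the last 8 weeks counted as retained, and without counting them. Record this addition in SAP section 4.

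The cost is SAP wording, a few extra table rows and a second retention figure that may be slightly lower. No new data are needed.
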